### **Introduction**

Parenteral nutrition (PN) is an important therapy in patients' recovery. It is indicated when the gastrointestinal tract is not functional or cannot be accessed, or the patients' nutrient needs are greater than those achieved using the gastrointestinal tract (1). Specific indications include complete intestinal obstruction, ileus or severe dysmotility, severe pancreatitis, high-output intestinal fistulae, short bowel syndrome or severe intestinal inflammatory disease (2,3).

It is important to indicate that PN need to be used in the appropriate setting, since it is a costly treatment and is not free of complications. Some of the complications secondary to PN are: catheter infections, hyperglycemia, hepatic dysfunction, hyperlipidemia and refeeding syndrome (2,4,5). Also, PN is associated with gut atrophy, reduced gut absorption, loss of gut barrier, altered gut microflora, increased bacterial adherence, increased microbe translocation, B and T cell dysfunction (3,6)

Bloodstream infections (BSI) rates vary widely among PN patients from 1.3-39% (7,8) even though there is evidence on how to reduce catheter-related infections (9). Still, there are studies that have found high rates of catheter-related infections in patients with parenteral nutrition. There is a cohort study in patients with central venous catheters, with or without PN, this study found that PN was an independent risk factor for BSI (10).

Another study in 19 Canadian hospitals found that the rates of BSI among patients with PN were 4 times higher than those not receiving PN (11). The most common organisms in hospitalized patients are coagulase-negative staphylococcus, *Staphylococcus aureus*, *Enterococcus*, *Candida* spp, *Klebsiella pneumoniae*, and *Pseudomonas aeruginosa* (8)

Until recently, Intralipid, a soybean oil-based lipid emulsion, has been the only available lipid for intravenous use in Canada. In 2010, ClinOleic, a new, predominantly olive oil based emulsion, has been approved by Health Canada as an alternative lipid.

There is an increasing need for hospitals to do quality-assurance studies for in-patient PN to assess indications, PN prescription, complications, clinical outcomes and costs. The only in-patient population that is well studied is the intensive care unit (ICU) population. Several meta-analyses showed that PN was associated with higher infection rate, longer length of stay and higher mortality when compared with enteral nutrition (12,13). Results from these and other studies were the basis for the Canadian ICU Guidelines (13-17).

The aims of this study (already approved CAPCR 12/5174/AE) ) were to determine if PN prescribed in in-patients follows existing guidelines in terms of timing of nutrition support, prescription and monitoring and, whether it is associated with complications. In addition, clinical outcomes such as length of stay and mortality are assessed.

In addition, we will evaluate, in this cohort of patients, the effect of 2 different lipid emulsions, both approved by Health Canada (Intralipid based on soybean oil and ClinOleic based on olive oil). These lipid emulsions, readily available through our provider, will be prescribed alternatively according to standards of care. We also plan to do additional measurements relevant to nutrition which include: C-reactive protein [CRP], pre-albumin, subjective global assessment, hand grip strength and arm circumference at beginning and 10 days of PN (or at discontinuation if less than 10days). We will also monitor diagnoses of infections during PN, including 1 week after PN discontinuation if patients remain in hospital. We were advised to re-submit as a new study rather than as an amendment.

## **Background**

In a prospective quality control study in Switzerland, 200 patients receiving PN were evaluated to see if PN prescription was justified according to the 2002 ASPEN guidelines. They were recruited during 18 weeks from Medicine, Surgery and Intensive Care Units. In this study, the Nutrition Support Team did not interfere with the PN prescriptions which were made by the medical staff of the different wards. They concluded that PN prescription was justified in all but 14 patients (7%). The energy supply was adequate only in 31.5% of the patients and overfeeding was more frequently observed. Women, thin and elderly patients were at more risk for overfeeding. The same happened with the protein supply, only 21% of the patients received an adequate supply and 65.5% received excess proteins. Also, 23.5% of the patients did not receive supplementation of vitamins and/or trace elements in their PN(18). This study shows the need to establish nutrition support protocols, particularly for PN.

In one Canadian study (19), the authors conducted a cross-sectional national survey of dietitians working in ICUs and identified interventions to target for quality improvement initiatives. In this study, 24% of the sites that responded reported the presence of a nutrition support team. The enteral route was the main route of administering nutrition support and of the 702 patients studied, 7.1% received parenteral nutrition only. Underfeeding seemed

to be a significant problem in the group of patients that stayed in the ICU for more than 3 days since 16% of these patients did not receive any nutrition support. Furthermore, of those that received nutrition support the average of calories and proteins received was 56% to 62% of their estimated needs over the first 12 days in the ICU. Another study conducted in Canadian ICUs evaluated whether an auditing practice and providing feedback is an effective strategy to improve adherence to nutrition guidelines. Twenty-six ICUs participated in an audit in 2007 and were given a feedback of their performance compared with the Canadian Critical Care Nutrition guidelines. The authors observed improvement in some nutrition practices in many ICUs after the reaudit in 2008 (20).

There is another study from Spain that shows the development and implementation of an audit tool for quality control of PN(21). In 1995, this quality control program was implemented by the Pharmacy Service and became a tool that measured compliance with accepted standards in the literature. The authors show the results of 5 audits during the past 10 years. This study was made in hospitalized patients with PN with the exception of ICU patients, pediatric patients and patients with chronic renal dysfunction. The authors concluded that in the last audit 9 out of 22 criteria reached the predefined standards, but also found some they needed to improve such as the indication of PN, assessment at the beginning of nutrition support and infectious complications.

The last study found(22), describes the approach taken by one hospital in California to improve safety and quality of PN. Process improvement strategies included revisions to the PN order form, education of clinicians, increased collaboration between pharmacists and registered dietitians and initiation of PN rounds. These process strategies positively impacted quality and costs. There was improvement in compliance with safe practice standards, percentage of patients with appropriate indication for PN, glycemic management, laboratory monitoring. The average number of patients receiving PN decreased from approximately 15 to less than 5 per day, this decreased the costs significantly.

In Canada, there are guidelines for nutrition support in mechanically ventilated critically ill adults. These guidelines were made by searching in four bibliographic databases randomized clinical trials or meta-analysis of randomized controlled trials that included any form of enteral or parenteral nutrition and the outcomes were: mortality, length of stay, quality of life, complications and cost. The search was done between the years 1980 to 2002. With respect to PN, the authors concluded that it should not be indicated until all strategies to maximize enteral nutrition delivery have been attempted. Also, when PN is indicated, glutamine should be used as a parenteral supplement if it is available. They also concluded that in patients who are not malnourished, are tolerating some enteral nutrition or when PN is indicated for short-term use (<10 days), hypocaloric PN and also withholding lipids should be considered in these specific setting. In surgical critically ill patients with

nutrition support, intensive insulin therapy to achieve blood glucose levels between 4.4 and 6.1 mmol/L should be considered(16)

The literature has mentioned that there is an overprescription of PN in patients with functional gastrointestinal tracts. It is important to mention that PN is associated with adverse events when compared to enteral nutrition. One review analyzed randomized clinical trials and concluded that there are more infections and longer lengths of stay in ICU patients receiving PN than those receiving enteral nutrition. Major complications such as: pneumothorax and air embolus are greater in parenterally fed patients. Also, the cost of PN is higher (6). Kudsk and colleagues reported pneumonia, abscesses, line infection or all three in 40% of parenterally fed patients versus 16% of enteral fed patients (23).

It is also known that PN is an expensive treatment and its cost differs among countries. In Europe, the daily cost of one compounded PN bag for neonates is around 55 Euros. An average cost per bag for infants <2 year was around 84 Euros. A major proportion of the cost is due to staff time(24). In the United States, when comparing compounded PN versus multi-chamber PN based on the underlying bloodstream infection risk the daily mean PN acquisition cost for patients receiving multi-chamber PN was US \$164 compared with US \$239 for patients receiving compounded PN(25). In Toronto General Hospital, the cost of a bag of parenteral nutrition is around \$140 CAD per day.

Intralipid is a soybean oil (SO) intravenous fat emulsion, available since 1961, rich in omega-6 polyunsaturated fatty acids (PUFA) and may enhance the generation of arachidonic acid-derived eicosanoids that could exaggerate the inflammatory response during stress and trauma (26). This pro-inflammatory effect may be detrimental. For example, in a prospective, randomized, controlled study comparing the vascular, metabolic, immune and inflammatory effects of 24h- infusion of parenteral nutrition (PN) with SO-based lipid emulsion (Intralipid), olive oil-based lipid emulsion (ClinOleic), lipid free and normal saline in 12 healthy subjects, the authors found that Intralipid increased blood pressure and altered endothelial function (27). A recent ASPEN position paper (28) reviewed the literature on lipid emulsions. While the current available, standard SO-based lipid emulsion like Intralipids meet the needs of most PN patients, alternative oil-based fat emulsions, like olive oil (OO) are used extensively in Europe and have been shown to be less proinflammatory and immunosuppressive due to different metabolic pathways. Patients receiving these alternative lipid emulsions may have better clinical outcomes but further research is needed to identify which type of lipid emulsion or which combination of oils may be most clinically useful for specific patient populations. SO lipid emulsions have plant sterols known as phytosterols, these are thought to alter hepatic function and have been associated with cholestasis in children on long-term PN (29,30). Also, most SO lipid emulsions have small amounts of  $\alpha$ -tocopherol, a known antioxidant. Studies have shown that vitamin E has a role in the prevention of hepatic injury in animal models(31), but there is still deficit in human data.

ClinOleic is a lipid emulsion composed of OO (80%) and SO (20%) (27,32). It is a third-generation of lipids and was introduced in Europe in the 1990s (28) . It has more monounsaturated fatty acids (MUFA) than PUFA, in a proportion of 65% MUFA and 20% PUFA (32). Even though it has a lower proportion of PUFA, no significant changes in plasma fatty acid profile and no deficiency of essential fatty acids have been reported (33). However, this was observed in a mouse model (34). ClinOleic is also rich in  $\alpha$ -tocopherol, and MUFA are resistant to lipid peroxidation so this intravenous lipid emulsion is potentially beneficial in subjects with risk of oxidative stress (32). There is a lack of studies that critically evaluate indications and outcomes regarding parenteral nutrition in different hospital units and in a wider variety of pathologies. There are very few studies published that compare two types of intravenous lipid emulsions and all have limited number of patients. There is a need to elucidate if the new lipid generations are a better option than the classic SO-based lipid emulsions and which patient populations will benefit most from them. This and our personal need for evaluating the indications and outcomes of patients with parenteral nutrition motivated us to do this study in our own center.

#### **Part A:**

#### **Primary Objective**

- To evaluate parenteral nutrition prescriptions in hospitalized patients
- **Secondary Objectives**
- Describe patient population according to the pathology that caused the hospitalization
- Record the indication that determined the need for PN and whether they are medical, surgical or ICU patients
- Assess updated Charlson co-morbidity index (CCI)
- Record the number of days with intakes less than 50% of requirements or NPO before PN was prescribed
- Perform a nutritional assessment which includes: weight at admission (if recorded in chart) and at time of starting PN, height, body mass index (BMI), Subjective Global Assessment (SGA), albumin and estimate of nutritional requirements.
- Record the initial PN prescription in terms of energy and proteins
- Record how many days it took to reach the nutritional requirements estimated by the dietitian
- Compare energy received as a goal with calculated energy requirements using published equations
- Record the number of times PN was interrupted
- Record the total number of PN days the patient received
- Determine the type of line (central or peripheral) and number of days with peripheral and/or central lines.

- Determine the type of vascular access (if central line)
- Record laboratory results once a week to assess potential metabolic complications associated with PN
- Record catheter related infections, whether suspected or confirmed
- Record any other complications deemed related to PN
- Record number of antibiotic-days to treat catheter-associated infections
- Record the reason why PN was discontinued
- Record total length of stay
- Record in-hospital mortality and cause of mortality during PN as well as during entire hospital stay

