### **Study design**

This is a prospective study that will evaluate the indications of parenteral nutrition in an inpatient setting. As part of their PN prescription, patients will receive either standard lipid (Intralipid) or OO-based lipid emulsion (ClinOleic), alternately depending on their time point of PN start, i.e. one person will receive Intralipid, the next one ClinOleic, etc. We will collect information from patients that have started with parenteral nutrition during their hospitalization and that are hospitalized in medical, surgical or ICU wards. We will also collect retrospective data of 100 patients to compare if the actions of the nutrition team and results change with respect to the prospective data.

Inclusion Criteria:

- Patients 18 years or older

- Patients that are expected to require PN for 5 days or more during their hospitalization
- Patients hospitalized in medical, surgical or ICU wards
- Signed informed consent either from the patient, their legally authorized representative or a direct family member

Exclusion Criteria:

- Patients without PN during their hospitalization

**Part A:** Patients will be approached when they start with PN during their hospitalization and will be followed until their last day of PN or, if occurred before PN ends, death. **Part**

**B:** For the proposed study, we will start PN as usual, according to the patients needs. We will randomly assign patients to receive either Intralipid or ClinOleic as the lipid emulsion in the PN. The amount of calories from the lipid emulsion will be equivalent.

Patients will be followed for one week after their last day on PN and, in addition, major outcomes such as mortality and length of stay will be assessed during the entire hospitalization.

Information regarding the patients nutrition will be obtained from the hospital chart and by direct communication with the PN team (dietitian, nurse, pharmacist) after signed informed consent.

We will analyze the nutritional indications and laboratory results of patients hospitalized in different units who are starting with PN alone or in combination with enteral or oral feeding twice a week. We will use a registry to enter the data.

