Measurements: :**Part A** 1) Patient demography: age, sex; 2) Type of patient: medical, surgical and/or ICU patients; 3) Type of any surgery the patient has during hospitalization; 4) Primary indications related to parenteral nutrition, comorbidities, updated CCI (31,32); 5) Nutritional assessment: weight, height, BMI, SGA, estimated energy and protein requirements; 6) comparison of energy received as a goal vs calculated energy requirements using published equations; 7) Energy, dextrose, aminoacids and lipids received by PN.

Total energy and proteins received including enteral nutrition and oral intake. Energy provided by Propofol, if received. In case of enteral nutrition, name and amount of product used; 8) Type of line used (peripheral or central); 9) Vascular access; 10) Reason for ending PN; 11) Number of times and reasons for interruption of PN; 12) Weekly PN related laboratory results; 13) Complications secondary to PN; 14) Outcome of patient

**Part B:** We will include the same measurements as in part A, but will add some additional nutritional parameters which will be done at baseline (Day 0) and after 10 days (Day 10)

with PN. Baseline or day 0 assessments to be done prior to or within 24 hours of PN initiation. Day 10 measurements to be done on day 10 of PN administration. If the PN ends before day 10, we will consider a cutoff at day 7 of PN. This means that if the PN ends before day 7, we will not repeat the measurements or blood work. If PN ends between days 7-9 we will repeat the measurements instead of doing them on day 10 for this special cases.

The parameters to measure will be: hand grip strength (kg), mid arm circumference (cm), SGA and weight as measures of nutritional status. We will also add hs-CRP, pre-albumin, and fatty acid profile in red blood cells (RBC) and plasma to the laboratory results at both time points. Clinical outcomes (documented infections, antibiotic-days or other adverse events) will be monitored for one week post-PN. In addition, mortality and length of stay will be documented for the entire hospitalization.

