## **Statistical analysis**

**Part A:** Descriptive statistics will be performed. Results will be expressed as absolute numbers and percentages, mean  $\pm$  standard deviation (SD) or median (minimum; maximum) depending on the variable types and distributions, separately for the prospective and the retrospective dataset.

For the prospective study, multivariate logistic regression will be performed to identify risk factors associated with specific PN prescription: for example, inadequate administration of PN. In addition, data from the prospective study and the retrospective chart review will be compared by unpaired t-test, Mann-Whitney-test or chi-square test as appropriate. A p value  $<0.05$  will be considered statistically significant. **Part**

**B:** For the Intralipid and the ClinOleic analysis, all variables will be tested for normal distribution (Shapiro Wilks test). *Primary outcome* is length of stay (in days). The Intralipid and ClinOleic groups will initially be compared with unpaired t-test or Mann-Whitney test as appropriate. *Secondary outcomes*: other clinical outcomes (days in ICU, antibiotic-days, infections, mortality) will also be analyzed the same way initially. For secondary outcomes that may change over time, i.e. hs-CRP, pre-albumin and other laboratory results, BMI, arm circumference, hand grip strength, changes will be compared between groups using unpaired t-test or Mann-Whitney test as appropriate. To account for possible covariate effects (eg. age, baseline BMI, Charlson comorbidity index), regression methods such as generalized linear models will be employed. All tests will be based on two-sided alternatives and a test will be considered statistically significant using alpha=0.05. SAS Enterprise Guide 4.1 software (SAS Institute Inc., Cary, NC, USA) will be used.

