## **Feasibility and Sample Size**

**Part A:** Based on previous studies, there are about 200 in-patients per year receiving PN. All patients will be assessed as per standard medical guidelines for PN and it is expected that 90% will agree to participate in the project. We calculate that we will have enrolled about 50 patients for Part A, before we start with part B. We will later include 150 more patients from Part B to have a total of 200 patients. We will compare the data obtained with 100 retrospective patients to see if the actions of the nutrition team changed since we started the project.

**Part B:** When we receive the ClinOleic in the hospital, patients will receive either SO-based lipid emulsion (Intralipid= 150 patients) or OO-based lipid emulsion (ClinOleic=150 patients) on an alternate basis (one-to-one) for the duration of the PN.

The total number of patients including part A and part B is estimated to be 350 patients. It is expected to take about one and a half years to recruit this number of patients.

For the Intralipid and ClinOleic analysis, we based our sample size on a study that evaluated the use of either SO or SO + fish oil (FO) in 206 patients with gastrointestinal or colonic cancer during 7 days after surgery and found that the patients that were given the FO treatment had significantly shorter length of stay than the SO group (Mean (SD) 15(5) versus 17(8) p= 0.041). Also, they had fewer infectious complications (50). Another study compared soybean oil and soybean oil+FO in 57 elderly patients with colorectal cancer. In the treatment group, there were fewer infectious complications and incidences of systemic inflammatory response syndrome (SIRS), and shorter lengths of hospital stay were observed(51).

Based on this, we estimate that a sample size of 150 in each group with a power of 0.8 and alpha of 0.05 will be sufficient to show a similar difference in length of stay between the two groups (soybean or ClinOleic) using the online sample size calculation provided by G.W. Snedecor & W.G. Cochran  
<http://www.biomath.info/power/ttest.htm>.

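### Days to reach nutritional requirements exists only for patients who reach them before PN stops, and the Part A analysis gives no place to those who never do

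*Combined protocol and SAP*

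**What the plan says.** The Part A list of secondary objectives includes "Record how many days it took to reach the nutritional requirements estimated by the dietitian". The same list records total PN days, the reason PN was discontinued, and mortality.

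Under Study design, Part A patients "will be followed until their last day of PN or, if occurred before PN ends, death". Part B adds a week after PN, which the protocol describes for infections, antibiotic-days and adverse events, not for intake.

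Entry depends on an expectation, not on an achieved duration: "Patients that are expected to require PN for 5 days or more during their hospitalization". The protocol foresees shorter courses. For the Part B measurements it says that "if the PN ends before day 7, we will not repeat the measurements or blood work".

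The Part A paragraph of Statistical analysis sets general rules for all variables: mean with SD, "or median (minimum; maximum) depending on the variable types and distributions, separately for the prospective and the retrospective dataset". It then says that "data from the prospective study and the retrospective chart review will be compared by unpaired t-test, Mann-Whitney-test or chi-square test as appropriate".

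Feasibility and Sample Size sets the prospective total ("We will later include 150 more patients from Part B to have a total of 200 patients") against 100 retrospective charts, to see whether the nutrition team's actions have changed. No section says how a patient who never reaches requirements is counted, whether requirements means energy, protein or both, whether PN alone or total intake counts, or how the retrospective charts are selected.

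**The concern.** Time to target is observed only if it does not exceed PN duration. A slow patient is more likely to run out of PN before reaching target, so the observed values lean towards the fast ones. A mean or median of these values is then too short, and it gets shorter as PN courses get shorter.

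This matters most for the comparison between periods. Days to target is one of the more direct measures of what the nutrition team does. If PN duration or the pattern of stopping differs between the prospective patients and the charts, part of any difference in days to target reflects that and not feeding speed. The prospective set is filtered by consent and by a bedside expectation of at least 5 PN days. No rule is given for the charts, so nothing in the plan makes the two sets comparable in PN duration.

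**Working it through.** The plan states no figure for days to target, attainment rate or PN duration, so there is none to reproduce. The check asks how a reachers-only summary behaves when true feeding speed is the same in both periods. T is the PN day on which target is reached and C is the last PN day; T is observed only if T ≤ C. All distributions below are assumptions.

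**1. Long-tailed time to target.** Let the daily chance of reaching target be p and, independently, the daily chance of PN stopping be q. Put r = (1−p)(1−q). Then:

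- proportion reaching = p / (1−r)
- mean T among reachers = 1 / (1−r)
- proportion of all starters at target by day 3 = p(1−r³) / (1−r)

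| True mean T | Mean PN | r | Reach target | Mean among reachers | At target by day 3 |
|---|---|---|---|---|---|
| 5 days (p = 0.2) | 10 days | 0.8 × 0.9 = 0.72 | 0.2/0.28 = 71% | 1/0.28 = 3.57 | 45% |
| 5 days | 6 days | 0.8 × 5/6 = 0.667 | 0.2/0.333 = 60% | 1/0.333 = 3.00 | 42% |
| 8 days (p = 0.125) | 10 days | 0.7875 | 59% | 4.71 | 30% |
| 8 days | 6 days | 0.729 | 46% | 3.69 | 28% |

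For a true mean of 5 days the gap is 3.57 − 3.00 = 0.57 days, or 19% of 3.00. For 8 days it is 4.71 − 3.69 = 1.02 days. Feeding speed is identical within each pair.

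**2. Short, narrow time to target.** Let T be 2, 3 or 4 days with equal chance, and keep the same PN distributions. The chance of still being on PN on day t is (1−q)^(t−1).

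- Mean PN 6 days: weights 0.833, 0.694, 0.579. Mean = (2×0.833 + 3×0.694 + 4×0.579) / 2.106 = 2.88 days.
- Mean PN 10 days: weights 0.900, 0.810, 0.729. Mean = (2×0.900 + 3×0.810 + 4×0.729) / 2.439 = 2.93 days.

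The true mean is 3.00, the gap is 0.05 days and the median is 3 in both. If every patient had at least 5 PN days, the gap would be zero.

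**3. A different model, by simulation.** T and C are log-normal with log-SD 0.6, rounded up to whole days: median T 3, 4 or 6 days, median PN 5, 7, 10 or 14 days, correlation −0.3, 0 or 0.3, with 1,000,000 draws per case. In all nine combinations of T and correlation, the mean among reachers fell as PN shortened and stayed below the true mean. For median T of 4 days and correlation 0 (true mean 5.29):

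| Median PN | 5 | 7 | 10 | 14 |
|---|---|---|---|---|
| Reach target | 66% | 78% | 88% | 94% |
| Mean among reachers | 4.01 | 4.36 | 4.68 | 4.92 |
| Median among reachers | 4 | 4 | 4 | 4 |

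For median T of 6 days the median among reachers moved by one day, from 5 to 6.

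**4. Effect on the tests.** 200 versus 100 patients, identical T, correlation 0, 4,000 trials per case. Two-sided testing is written in the Part B paragraph ("All tests will be based on two-sided alternatives and a test will be considered statistically significant using alpha=0.05") and is assumed here for Part A. Ranges are over median T of 3 to 6 days.

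| Median PN, prospective vs retrospective | t-test rejects | Mann-Whitney rejects |
|---|---|---|
| 10 vs 10 | 4–5% | 4–5% |
| 7 vs 10 | 14–29% | 11–24% |
| 7 vs 14 | 28–68% | 19–58% |
| 5 vs 10 | 47–79% | 35–72% |

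**5. Equal PN duration.** With median PN of 10 days in both periods, a true gap of 7.68 − 5.29 = 2.39 days appears among reachers as 6.19 − 4.68 = 1.51 days. The false-positive rate is then nominal, but a real difference is attenuated.

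**The case against.** The analysis of this variable is inferred from general rules. Statistical analysis does not name days to target and does not say that patients without a value are dropped. A chi-square test on reached versus not reached, or a Mann-Whitney test with non-reachers ranked last, would both fit the wording. This stands: the fault is that the plan gives these patients no place, not that it orders their exclusion. A day count handled in the ordinary way would still leave them out.

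A reader might infer that the comparison between periods is biased. The documents do not support that. A false difference needs PN duration or stopping pattern to differ between the cohorts, and they neither show nor exclude it.

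A reader might also take 19% as the expected distortion. It comes from a long-tailed model in which 1 − (5/6)⁴ = 52% of patients with mean PN of 6 days stop before day 5, which fits poorly with entry on an expectation of 5 or more days. The only ramp-up time in the documents, quoted from an ICU guideline in the energy-equation paragraph, is 2 to 3 days. With a range close to that, the gap nearly vanishes.

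Nor may non-reachers be called the patients with the worst delivery. PN may stop because oral or enteral intake has recovered.

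Finally, the overall proportion reaching target also depends on PN duration (66% to 94% above, with identical speed). That is true, but with all starters in the denominator shorter PN shows as fewer patients reaching target, instead of passing for faster feeding.

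**Conclusion.** The point holds in a limited form. Analysed as an ordinary day count, days to requirements describes only patients who reached target while on PN, and it understates time to target whenever PN stops some patients first. It can create or mask a difference between periods if PN duration or stopping differs. If they do not differ, it can still shrink a real one.

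The size cannot be fixed from the documents. Under the models above with mean PN of 6 versus 10 days, the spurious gap in means runs from about 0.05 days to 0.6 days or more. The whole-day median moves less, and the effect is negligible if nearly all patients reach target within a few days.

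This is one of 19 Part A secondary items, with no hypothesis or power attached. Adequacy of PN is also assessed in other ways. It is a worthwhile improvement, not a threat to the study's main results.

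**What to change.** In the Part A paragraph of Statistical analysis:

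1. Define reaching requirements: energy, protein or both, and PN alone or total intake.
2. Report the number and proportion reaching them by a fixed PN day, among all PN starters.
3. Base the prospective-versus-retrospective comparison on the cumulative incidence of reaching requirements from PN start (Aalen-Johansen estimate, Gray's test). Treat PN stop, split by recorded reason including recovery of oral or enteral intake, and death as competing events. Show the curves for stopping beside it, since the incidence of reaching target depends on them.
4. Keep days among reachers as a descriptive figure only, always with the number not reaching.
5. Apply one selection rule to both cohorts as far as the charts allow. Confirm that the day target was reached, PN start and stop dates, and stop reason can be extracted from the retrospective charts.

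Prel. cost: the prospective data are already planned (days to requirements, total PN days, reason for stopping, death). Availability in the charts is not confirmed by the protocol. The downside is slightly more analysis, and a proportion and a curve in place of a single mean.
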